2.2.1 Randomization and drug dispensing irregularities

Randomization and drug-dispensing irregularities occur whenever:

1. A randomization is not in accordance with the protocol-defined randomization method, such as a) an ineligible patient is randomized, b) a patient is randomized based on an incorrect stratum, c) a patient is randomized twice, or d) in a dynamic randomization scheme the treatment assignment is, in fact, not random, due to a computer program error.
OR
2. A patient is dispensed an IMP kit not allocated by the protocol-defined randomization, such as a) a patient at any time in the study is dispensed a different treatment kit than as randomized (which may or may not contain the correct-as-randomized IMP), or b) a nonrandomized patient is treated with IMP reserved for randomized patients.

Randomization and drug-dispensing irregularities will be monitored throughout the study and reviewed on an ongoing basis.

All randomization and drug-dispensing irregularities will be documented in the CSR. If the number of irregularities is large enough to make a tabular summary useful, the irregularities will be categorized and summarized among randomized patients (number and percentages). Nonrandomized, treated patients will be described separately.

Randomization and drug-dispensing irregularities to be prospectively identified include but are not limited to:

Table 7 - Randomization and Drug Allocation Irregularities

Randomization and Drug Allocation Irregularities
Kit dispensation without IVRS transaction
Erroneous kit dispensation
Kit not available
Randomization by error
Subject randomized twice
Forced randomization
Subject switched to another site

IVRS=Interactive Voice Response System

2.3 ANALYSIS POPULATIONS

The randomized population includes any patient who has been allocated to a randomized treatment regardless of whether the treatment kit was used.

Patients treated without being randomized will not be considered randomized and will not be included in any efficacy population.

For any patient randomized more than once, only the data associated with the first randomization will be used in any analysis population. The safety experience associated with any later randomization will be assessed separately.

The safety experience of patients treated and not randomized will be reported separately, and these patients will not be in the safety population.

2.3.1 Efficacy populations

Week 52 Analysis set: The primary endpoint for the study is sustained remission at Week 52. Based on patients' enrollment dates and the study discontinuation plan, not all the patients had an opportunity to complete the 52-week treatment period. For the cohort of patients who did not have an opportunity to complete the 52-week treatment period, it is not meaningful to define the endpoint of sustained remission at Week 52. Therefore, the analysis of primary endpoint will be limited to the Week 52 Analysis set, which includes the cohort of patients who had an opportunity to complete the 52-week treatment period. This cohort of patients is defined as the patients with a randomization date prior to *Oct 16, 2019* (i.e., *Oct 13, 2019*+3 days IMP administration time window, where *Oct 13, 2019* is 1-year before the targeted last patient last EOT visit date [i.e., *Oct 13, 2020*] according to the study discontinuation plan), which contains a total of 36 patients (out of 83 randomized patients).

For the same reason, the analysis of secondary endpoint of cumulative GTI scores at Week 52 will also be limited to the cohort of patients who had an opportunity to complete the 52-week treatment period.

For the rest of the efficacy endpoints, the primary analysis population will be the ITT population as defined in [Section 2.3.1.1](#).

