1 OVERVIEW AND INVESTIGATIONAL PLAN

This statistical analysis plan (SAP) provides a comprehensive and detailed description of statistical strategy and methodology to be used to analyze the data from sarilumab EFC15068 study in patients with giant cell arteritis (GCA).

Due to the ongoing pandemic of COVID-19 (the disease caused by the novel coronavirus), the operations of sarilumab (Kevzara®) clinical trial EFC15068 have been significantly disrupted in various countries and sites. Consequently, the screening/recruitment activities for this study have been suspended since 19th of March 2020. Due to the protracted recruitment timeline and internal portfolio reprioritization, in July 2020, Sanofi has decided not to re-open the screening/recruitment activities and to discontinue the study. This decision is not related to any safety issues arising from the administration of sarilumab.

A total of 83 patients (out of 360 planned patients) have been randomized in the study. While the number of randomized patients may not be adequate to demonstrate a statistically significant benefit, the data generated from the treated patients may contribute to the further understanding of IL-6 signaling blockade in this disease state.

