During the course of study, for patients in need of rescue therapy as per Investigator judgment, CS should be the agent of first choice. Patients may continue SC administration of sarilumab or matching placebo only if CS is used as the rescue therapy. If the patients remain symptomatic despite CS rescue therapy, then other treatment options including nonbiological immunosuppressive drugs may be used and the patient must be discontinued from the study treatment and considered a non-responder.

If the patient or Investigator decides to discontinue the administration of blinded sarilumab injections, then the patient will be asked to return to the site for study assessments as per protocol until end of study (EOS) evaluation, unless the patient cannot or does not wish to continue the assessments, in which case an early withdrawal visit and safety follow up should be performed. It is recommended that patients complete Visit 13, if possible.

Total duration of study participation for each patient is up to 82 weeks:

- Up to 6 weeks screening period.
- 52-week treatment period (sarilumab or placebo, double-blind phase).
- 24-week post treatment follow-up period.

The last patient last visit will occur when the last patient has completed the 24-week follow up period (EOS). The end of the clinical trial is defined as the last patient's last visit.

Study discontinuation plan

As mentioned in [Section 1](#), due to the protracted recruitment timeline and internal portfolio reprioritization, Sanofi has decided to terminate the EFC15068 study in July 2020. For patients who were already enrolled with ongoing treatment in the study, investigators were instructed to discontinue the study drugs and transition these patients into post-treatment follow-up period for safety assessments. The study discontinuation plan is as follows:

- All randomized patients should stop by 12 weeks from the date of announcement to the sites and should be scheduled for the end of study treatment visit at their earliest

convenience and no later than *October 13, 2020*, which would ensure sufficient time for patients to identify alternative therapy as needed.

- All patients will have a follow-up (EOS) visit that is 6 weeks after treatment cessation and no later than *November 24, 2020*.

Thus, the last patient last visit will occur when the last patient has completed the 6-week follow-up period (EOS). The end of the clinical trial is defined as the last patient's last visit.

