1.3 DETERMINATION OF SAMPLE SIZE

The sample size calculations are based on the primary efficacy variable of sustained remission at Week 52. Data from another trial that evaluated the safety and efficacy of tocilizumab in a similar population show that the expected event rate in Group C (placebo with 26-week taper, n = 60) is 14% and in Group D (placebo with 52-week taper, n = 120) is 18% (1). Assuming a treatment difference of 40% and a significance level of 0.01 (2-sided) this will ensure that all comparisons of the primary endpoint in Group A (sarilumab 200 mg, n = 120) and Group B (sarilumab 150 mg, n = 60) compared to the 2 control groups will have at least 90% power. The sample size has also been selected to ensure adequate power for sensitivity analyses excluding acute phase reactants from the primary endpoint definition.

The above calculations were for the full enrollment. However, the number of randomized patients is 83 in 4 arms at the time of the premature termination of the study. In addition, based on patients' enrollment dates and the study discontinuation plan, only about 36 patients (out of 83) had an opportunity to complete the 52-week treatment period. For the cohort of patients who did not have an opportunity to complete the 52-week treatment period, it is not meaningful to define the endpoint of sustained remission at Week 52. Therefore, the analysis of primary endpoint will be limited to the cohort of patients who had an opportunity to complete the 52-week treatment period. Due to the small number of patients (n=36) in this cohort (see Section 2.3.1 for definition of the cohort), the powers on the primary endpoint are minimal. As a result, all the efficacy analyses will be descriptive in nature and all reported p-values will be nominal for the study.

Based on patients' enrollment dates, all enrolled patients (n=83) had an opportunity to complete at least 24 weeks of treatment, therefore, an additional endpoint, sustained remission at Week 24 is added in the SAP (see Section 2.1.3.1 for the detail definition). Table 1 provides the power calculations on the additional endpoint of sustained remission at Week 24. Due to the small number of patients in each individual treatment group, the power calculations were also provided for the comparison between the combined sarilumab groups (i.e., Group A+B) and the combined placebo groups (i.e., Group C+D) assuming the same effect sizes as mentioned above.

Table 1: Updated power calculations

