1.6 STATISTICAL MODIFICATIONS MADE IN THE STATISTICAL ANALYSIS PLAN

Due to the early termination of the study and study discontinuation plan, a large amount of data will not be able to be collected since many enrolled patients will not complete all planned study visits and study procedures for the assessments of efficacy, ADA, and biomarker endpoints. In addition, the number of randomized patients is 83 in 4 arms (out of 360 planned) at the time of the premature termination of the study. The changes from the statistical analysis plan outlined in the protocol are summarized below.

- The primary endpoint for the study is sustained remission at Week 52. Based on patients' enrollment dates and the study discontinuation plan, only about 36 patients (out of 83) had an opportunity to complete the 52-week treatment period. For the cohort of patients who

did not have an opportunity to complete the 52-week treatment period, it is not meaningful to define the endpoint of sustained remission at Week 52. Therefore, the analysis of primary endpoint will be limited to the cohort of patients who had an opportunity to complete the 52-week treatment period. Details can be found in [Section 2.1.3.1](#) and [Section 2.4.4.1](#).

- Based on patients' enrollment dates and the study discontinuation plan, all patients should have had the opportunity to be treated for at least 24 weeks, so an additional endpoint, sustained remission at Week 24, is added in the SAP. Details can be found in [Section 2.1.3.1](#).
- Due to the same reason as mentioned above, the secondary endpoints of cumulative GTI scores at Week 52 will be limited to the cohort of patients who had an opportunity to complete the 52-week treatment period. In addition, the cumulative GTI scores will also be assessed at Week 24. Details are provided in [Section 2.1.3.2](#).
- The missing data imputation strategy for defining the endpoints of sustained remission at W24 and W52, and cumulative GTI scores at W24 and W52 can be found in [Section 2.1.3.1](#) and [Section 2.1.3.2](#), respectively; the rest of efficacy analyses will be based on data as observed, no missing data will be imputed.

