Appendix C Summary of statistical analyses

Endpoint	Analysis		Statistical	Supportive	Subgroup	Other
	Population	Primary Analysis	Method	Analysis*	Analysis*	Analyses*
Primary Endpoint						
Patients who achieved sustained remission at Week 52	ITT	Proportion of patients achieving sustained remission at Week 52	CMH test stratified by baseline prednisone dose for combined groups, and descriptive analysis for non-combined groups.	1) Sensitivity analysis;2) Analysis excluding patients who prematurely withdraw from the study due to early termination of the study	No	No
Additional endpoint: Patients who achieved sustained remission at Week 24	ITT	Proportion of patients achieving sustained remission at Week 24	CMH test stratified by baseline prednisone dose for combined groups, and descriptive analysis for non-combined groups	Sensitivity analysis	No	No
Secondary Endpoints						
Patients who achieved of disease remission by Week 12	ITT	Proportion of patients who achieved of disease remission by Week 12	Descriptive	No	No	No
Patients who have absence of disease flare from Week 12 through Week 24 and Week 52	ITT	Proportion of patients who have absence of disease flare from Week 12 through Week 24 and Week 52	Descriptive	No	No	No
Patients who have normalization of CRP (decrease to <10 mg/L) with sustained normalization from Week	ITT	Proportion of patients who have normalization of CRP (decrease to <10 mg/L) with sustained normalization from Week 12 through Week 24 and Week 52	Descriptive	No	No	No

Endpoint	Analysis		Statistical	Supportive	Subgroup	Other
	Population	Primary Analysis	Method	Analysis*	Analysis*	Analyses*
12 through Week 24 and Week 52						
Patients who successfully adhere to the prednisone taper from Week 12 through Week 24 and Week 52	ITT	Proportion of patients who successfully adhere to the prednisone taper from Week 12 through Week 24 and Week 52	Descriptive	No	No	No
Total cumulative prednisone (or equivalent) dose	ITT	Total cumulative prednisone (or equivalent) dose over 52-week treatment period	Descriptive	No	No	No
Time to the first GCA flare after clinical remission up to Week 52	ITT	Time (from randomization) to the first GCA flare after clinical remission up to Week 52	Kaplan-Meier estimates and Cox proportional hazards model for combined groups, and descriptive analysis for non-combined groups.	No	No	No

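### The Week 52 composite is analysed in 36 of 83 randomised patients; a supplementary time-to-loss analysis in all 83 would estimate it more precisely at little cost

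*SAP*

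**What the plan says.** SAP section 1 reports that "A total of 83 patients (out of 360 planned patients) have been randomized in the study". SAP 2.3.1 defines the Week 52 Analysis set by randomisation before 16 October 2019, "which contains a total of 36 patients (out of 83 randomized patients"), and says that "the analysis of primary endpoint will be limited to the Week 52 Analysis set". The reason, given in SAP 1.3 and repeated elsewhere, is that for the remaining patients "it is not meaningful to define the endpoint of sustained remission at Week 52". SAP 2.4.4.1 then compares combined sarilumab with combined placebo in this set by a stratified CMH test.

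The other 47 are not dropped from the trial. SAP 1.6 says "all patients should have had the opportunity to be treated for at least 24 weeks" and adds sustained remission at Week 24, analysed in ITT. SAP 2.3.1 assigns the remaining efficacy endpoints to ITT (cumulative GTI scores at Week 52 excepted), so time to first flare and cumulative steroid dose also use all 83.

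Three other provisions matter:
- SAP 1.1 says that patients "should be scheduled for the end of study treatment visit at their earliest" convenience, and by 13 October 2020 at the latest.
- SAP 2.1.3.1 counts any permanent treatment stop before Week 52 as failure of components 2 to 4, with no exception for the sponsor's termination.
- SAP Appendix C gives ITT as the population for the Week 52 endpoint and lists as a supportive analysis an "Analysis excluding patients who prematurely withdraw from the study due to early termination of the study".

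**The concern.** The Week 52 binary outcome is undefined only for a later patient who was still in sustained remission when the sponsor stopped treatment. A later patient who was not in remission by Week 12, or who flared at Week 20, has already failed. The former is an ordinary censored observation; the latter is a known failure. Leaving both out of the composite uses less information than the trial collected.

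The planned ITT analyses do not replace what is missing. Week 24 is early: in the 26-week taper of protocol Appendix B, patients who started at 50 or 60 mg are still scheduled for 1 mg at Week 24, and the other starting doses have been at placebo for 0 to 4 weeks. Protocol 6.5 asks whether remission holds to Week 52. Time to first flare (SAP 2.1.3.2) does follow remitters past the taper, but it takes no account of CRP failure and censors patients who never remit at randomisation, so they add nothing.

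What is at stake is the width of the interval around the trial's main efficacy estimate.

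**Working it through.** **Reproducing the SAP.** Two-sided chi-square power with pooled null variance gives 0.823 (alpha 0.01) and 0.945 (alpha 0.05) for 42 versus 41 patients at 53% and 17%. SAP Table 1 states 82.3% and 94.5%. The other eight powers in that table also reproduce.

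**Who is excluded.** 83 - 36 = 47, and 47/83 = 56.6%. A patient randomised on 15 October 2019 reaches Day 365 on 13 October 2020; one randomised a day later reaches Day 364. The rule is therefore purely by calendar.

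**Precision of the planned analysis.** The arm split of the 36 is not given, so I assume 18:18. SD of the Week 52 difference = sqrt(0.53 × 0.47/18 + 0.17 × 0.83/18) = sqrt(0.3902/18) = 0.147, an approximate 95% half-width of 1.96 × 0.147 = 0.29. The same chi-square formula gives power 0.63 at alpha 0.05 (0.59 to 0.63 for splits from 14:22 to 22:14). The SAP calls the power minimal and gives no figure.

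**Precision using all 83.** Simulation, 2,000 runs per row, Week 52 rates fixed at 53% and 17%. Non-remission is an event at Week 12, the 36 are followed to Week 52, and the 47 are censored uniformly over the range shown. The documents give neither the share failing at Week 12, nor the hazard shape, nor the actual follow-up; these are assumptions.

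| Assumed failure pattern | Follow-up of the 47 (weeks) | SD, n=36 | SD, Kaplan-Meier n=83 | Reduction |
|---|---|---|---|---|
| 20% of failures at Week 12, then constant hazard | 24–52 | 0.150 | 0.116 | 23% |
| same | 24–32 | 0.146 | 0.131 | 10% |
| 40% at Week 12, then constant | 24–52 | 0.152 | 0.114 | 25% |
| same, failures dated only to visits | 24–52 | 0.146 | 0.122 | 16% |
| 60% at Week 12, then constant | 29.7–51.9 | 0.145 | 0.105 | 28% |
| Week 12 remission 80% in both arms, then constant | 12–40 | 0.147 | 0.127 | 14% |
| Week 12 remission 70% in both arms, relapse only from Week 26 | 18–40 | 0.147 | 0.127 | 14% |

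The mean Kaplan-Meier difference stayed close to the true 0.36, so the method is not visibly biased when censoring is independent. An SD from 2,000 runs has relative error of about 1/sqrt(4,000) = 1.6%, so the ends are good to a point or two. I state the gain as roughly 11 to 27%. At 27% the SD is 0.147 × 0.73 = 0.107 and the half-width about 0.21; at 11% they are 0.131 and about 0.26.

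**Log-rank is less dependable.** With constant hazard after Week 12 and at least 24 weeks of follow-up, log-rank power on 83 patients is 0.88 to 0.93 at alpha 0.05. In the last row it falls to about 53 to 55%, below the 63 to 65% simulated for the n=36 test, because few of the late events are seen.

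**How far censoring is by calendar.** SAP 1.1 gives 12 weeks from the announcement to the latest stop, which puts the announcement near 21 July 2020 (13 October minus 84 days). A patient randomised on 19 March 2020, when recruitment was suspended, had 29.7 weeks to 13 October but only 17.7 weeks if stopped at the announcement. The 24 weeks in the SAP is opportunity, not guaranteed follow-up.

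**The case against.** The strongest reply is that the plan is open about its limits. Restriction by randomisation date is not related to outcome, the SAP calls all efficacy analyses descriptive and all p-values nominal, and the 47 contribute to three ITT analyses. All of this stands. A reader might infer that the comparison is biased or that the later patients' data are ignored; the documents support neither.

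A reader might also infer that censoring is non-informative because termination was a sponsor decision. The documents do not go that far. Patients could stop at any time up to 13 October 2020, with the window meant to let them find other treatment, so disease status could have influenced when they stopped.

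A third objection is that separating sponsor-termination stops from other withdrawals uses a post-randomisation reason, as Appendix C's supportive analysis does. That is partly right. Censoring keeps each patient's follow-up and any earlier failure, whereas exclusion removes the patient, but both depend on the reason being classified correctly.

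Finally, the size of the gain depends on assumptions outside the documents. That stands too, and rules out a single headline figure for power or equivalent sample size.

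**Conclusion.** The point holds as an inexpensive improvement, not as an error that invalidates the plan. No planned analysis dates loss of the four-part composite through Week 52, and 47 of 83 patients therefore add nothing to that estimate. Kaplan-Meier on all 83 was more precise in every scenario run, by roughly 11 to 27% in the SD of the Week 52 difference. This rests on the SAP's 53% and 17%, an even split of the 36, independent censoring, and the assumed Week 12 rates, hazard shapes and follow-up. The log-rank test does not gain in every scenario and should not carry the analysis.

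**What to change.** Keep the n=36 table and add to SAP 2.4.4.1 a supplementary ITT (n=83) analysis of time to loss of sustained remission:

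- **Event:** non-remission, counted at Week 12; the first later failure of any component; or treatment withdrawal not caused by the sponsor's termination.
- **Censoring:** sponsor-termination stops at the actual stop date; otherwise Week 52. The rule in SAP 2.1.3.1 that any earlier stop is a failure needs an exception here. The exception also covers any of the 36 who stopped on the sponsor's instruction before their own Week 52.
- **Main output:** Kaplan-Meier estimates at Weeks 24, 40 and 52 for combined sarilumab and combined placebo, and their difference with 95% CI.
- **Secondary output:** log-rank test stratified by baseline prednisone dose.
- **Sensitivity to informative censoring:** for example, count sponsor-termination stops as failures in patients with active disease at the last visit, or censor everyone at the announcement date, which the SAP should then state.

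Reconcile Appendix C with SAP 2.3.1 on the population for the Week 52 endpoint. State the population for the Week 52 component tables as well. Read literally, they are in ITT, and 2.1.3.1 would count sponsor-stopped patients as failures of components 2 to 4.

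The cost is SAP text and one derived dataset; Kaplan-Meier and Cox are already planned for flare, and no new data are needed. The downsides are that CRP failures are dated only to the visit, that the reason for stopping must be classified, and that the Week 52 tail rests on at most the 36 early patients still at risk.

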Successful adherence to the prednisone taper from Week 12 through Week 52 is defined as patients did not take rescue therapy from Week 12 through Week 52 and may include the use of any excess prednisone (beyond the per protocol CS tapering regimen) with a cumulative dose of ≤100 mg (or equivalent), such as those employed to manage AE not related to GCA. The cumulative dose of excess prednisone use will be counted from baseline to Week 52.

In addition, patients who permanently withdraw from the study treatment prior to Week 52 will be considered as not achieved component 2, 3, or 4 for the primary endpoint.

Additional Endpoint: Sustained remission at Week 24

Based on patients’ enrollment dates and the study discontinuation plan, all patients would have had the opportunity to be treated for at least 24 weeks. As a result, an additional endpoint, sustained remission at Week 24, which is defined similarly as the primary endpoint but with shorter sustained period, is added in the SAP.

The sustained remission at Week 24 is defined by having met all of the following parameters:

- Achievement of disease remission not later than Week 12,
- Absence of disease flare from Week 12 through Week 24,
- Normalization of CRP (to <10 mg/L, with an absence of successive elevations to ≥10 mg/L) from Week 12 through Week 24, and
- Successful adherence to the prednisone taper from Week 12 through Week 24.

Components of the sustained remission at Week 24 are described as below:

- 1. Achievement of disease remission not later than Week 12**, which is defined in the same way as described for the primary endpoint.
- 2. Absence of disease flare from Week 12 through Week 24**, where disease flare is defined in the same way as described for the primary endpoint.
- 3. Normalization of CRP (to <10 mg/L, with an absence of successive elevations to ≥10 mg/L) from Week 12 through Week 24**

The status of normalization of CRP from Week 12 through Week 24 will be determined based on the CRP values measured at Week 16, Week 20, Week 24. If there are two or more consecutive visits with CRP ≥10 mg/L, then it's categorized as no normalization of CRP. Intermittent missing CRP at Week 16, Week 20 or Week 24 will be imputed using last value carried forward (LOCF) approach.

4. Successful adherence to the prednisone taper from Week 12 through Week 24

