Successful adherence to the prednisone taper from Week 12 through Week 24 is defined as patients did not take rescue therapy from Week 12 through Week 24 and may include the use of any excess prednisone (beyond the per protocol CS tapering regimen) with a cumulative dose of ≤100 mg (or equivalent), such as those employed to manage AE not related to GCA. The cumulative dose of excess prednisone use will be counted from baseline to Week 24.

In addition, patients who permanently withdraw from the study treatment prior to Week 24 will be considered as not achieved component 2, 3, or 4 for the primary endpoint.

Blinding of CRP and ESR assessment results

Investigators, including Efficacy Assessors, and patients will remain blinded to CRP and ESR results (except screening and baseline). Safety Assessors will also be blinded on post baseline CRP but will have access to ESR results.

ESR kits will be provided by the central laboratory while the test will be performed locally at site, results (the distance in millimeters (mm) that red blood cells has descended in 1 hour) will be blinded to Investigators including Efficacy Assessors and staff directly involved in efficacy assessment of study patients.

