2.1.3.2 Secondary efficacy endpoint(s)

The following efficacy variables will be assessed:

- Components of sustained remission composite measure at Week 52 and Week 24
- Total cumulative corticosteroid (including prednisone) dose over during the treatment period
- Time to first GCA flare during the treatment period

- GTI Cumulative worsening score (CWS) and Aggregate improvement score (AIS) at Week 52 and Week 24.

Below are descriptions of these variables. Details related to imputation of GTI scores are described in [Section 2.5.2](#).

Components of sustained remission composite measure at Week 52

1. Proportion of patients who achieved disease remission by Week 12.
2. Proportion of patients who have no disease flare from Week 12 through Week 52.
3. Proportion of patients who have normalization of CRP (to <10 mg/L, with an absence of successive elevations to ≥ 10 mg/L) from Week 12 through Week 52.
4. Proportion of patients who successfully adhere to the prednisone taper from Week 12 through Week 52.

Components of sustained remission composite measure at Week 24

1. Proportion of patients who achieved disease remission by Week 12.
2. Proportion of patients who have no disease flare from Week 12 through Week 24.
3. Proportion of patients who have normalization of CRP (to <10 mg/L, with an absence of successive elevations to ≥ 10 mg/L) from Week 12 through Week 24.
4. Proportion of patients who successfully adhere to the prednisone taper from Week 12 through Week 24.

Total cumulative corticosteroid (including prednisone) dose during the treatment period

The total cumulative corticosteroid includes prednisone taper regimen per protocol, use of prednisone (an excess of ≤ 100 mg of prednisone during the study treatment period such as those employed to manage AE not related to GCA is permissible for meeting the definition of maintenance of sustained remission) and rescue corticosteroids dose prescribed for rescue therapy over the treatment period for GCA disease only.

Time to first GCA flare during the treatment period

The duration (in days) from randomization to first GCA flare after clinical remission and up to 52 weeks. Patients who never achieve remission will be censored at randomization day; and those who achieved clinical remission and never flared will be censored at the end of treatment assessment date up to Week 52.

The definition of GCA flare is provide in [Section 2.1.3.1](#) primary efficacy endpoint.

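### Week 52 components 2 to 4 are left in ITT (83 patients) while the composite they explain is restricted to 36, so they cannot decompose it

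*SAP*

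**What the plan says.** The SAP was rewritten after the sponsor ended the study early. Section 1.1 states: "All randomized patients should stop by 12 weeks from the date of announcement to the sites". It sets 13 October 2020 as the latest end-of-treatment visit. Section 1.3 records the consequence: "only about 36 patients (out of 83) had an opportunity to complete the 52-week treatment period".

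Section 2.3.1 reasons that for the remaining patients "it is not meaningful to define the endpoint of sustained remission at Week 52", and defines a Week 52 Analysis set of 36 patients, randomised before 16 October 2019. It names two analyses for that set: the Week 52 composite and the Week 52 cumulative GTI scores (CWS and AIS). Then: "For the rest of the efficacy endpoints, the primary analysis population will be the ITT population".

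Section 2.1.3.2 lists "Components of sustained remission composite measure at Week 52 and Week 24" among the secondary efficacy endpoints. The components are (1) remission by Week 12, (2) no flare, (3) CRP normalisation and (4) taper adherence, with the last three running from Week 12 to the endpoint week. Section 2.4.4.2 asks for counts and percentages by treatment group and names no population for them. The same section does restate the restriction for Week 52 CWS and AIS. Appendix C lists ITT for all four components.

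On early stopping, section 2.1.3.1 says that patients who permanently stop study treatment "prior to Week 52 will be considered as not achieved component 2, 3, or 4 for the primary endpoint". A parallel rule covers stopping "prior to Week 24 will be considered as not achieved component 2, 3, or 4 for the primary endpoint". Section 1.6 points to 2.1.3.1 and 2.1.3.2 for missing data in the sustained-remission and cumulative GTI endpoints, and adds: "the rest of efficacy analyses will be based on data as observed, no missing data will be imputed".

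**The concern.** The components are there to show which part of the composite drove the result. That works only if they are measured in the same patients under the same rules. Here the composite is to be computed in 36 patients and its Week 52 components in 83, most of whom could not be followed on treatment to Week 52. The SAP's argument that a Week 52 outcome has no meaning for those patients holds just as well for flare, CRP and taper adherence through Week 52.

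If 2.3.1 is followed as written, the Week 52 component percentages will largely reflect randomisation date, or an unstated choice about how to treat truncated follow-up. A reader could see a composite rate above the rate of one of its own components, which cannot happen within a single population.

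**Working it through.** **Inputs.** ITT is all randomised patients, 83 (SAP 1 and 2.3.1.1). The Week 52 Analysis set has 36 (2.3.1). Group sizes A, B, C, D are 28, 14, 14, 27 (SAP Table 1). Planned Week 52 sustained-remission rates are 54% for Group A and 50% for Group B (protocol 11.1). The last end-of-treatment date is 13 October 2020 (SAP 1.1).

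**Step 1: the plan's own figures.** 28 + 14 + 14 + 27 = 83. Randomisation on 15 October 2019 plus 364 days puts Day 365 on 13 October 2020, so the cut-off agrees with the discontinuation plan. The count of 36 cannot be rechecked without randomisation dates. Outside the set: 83 − 36 = 47. This is approximate for the present purpose, because with the 3-day visit window patients randomised on 16 to 18 October 2019 could still have an in-window Week 52 visit by 13 October 2020.

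**Step 2: ITT with the withdrawal rule.**
- Failed because of randomisation date: 47/83 = 56.6%.
- Highest possible rate for each of components 2 to 4: 36/83 = 43.4% overall, below both planned composite rates.
- By group, the SAP does not give the split of the 36. Assuming it is proportional: 36 × 28/83 = 12.1, 36 × 14/83 = 6.1 (B and C), 36 × 27/83 = 11.7, so 12, 6, 6, 12. The caps are 12/28 = 42.9%, 6/14 = 42.9% (B and C) and 12/27 = 44.4%.
- Range for Group A: 9 to 15 of the 36 gives 9/28 = 32.1% to 15/28 = 53.6%; the cap passes 54% only at 16 or more (16/28 = 57.1%). For Group B, 4 to 8 gives 4/14 = 28.6% to 8/14 = 57.1%, reaching 50% at 7.
- Example: with 12 Group A patients in the Week 52 set, a composite near 54% is 6/12 = 50.0% or 7/12 = 58.3%. Either exceeds the 42.9% ceiling on its components.

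**Step 3: ITT with data as observed.** Two versions are possible, and the SAP does not choose between them.
- If all 47 count as missing, section 2.5.3 leaves them out of the percentage. The same successes are divided by 36 instead of 83, a figure 83/36 = 2.3 times as large as in Step 2. This is the extreme case: a flare or rescue after Week 12 but before stopping would be an observed failure, not a missing value.
- If the 47 are judged on the follow-up they have, they are at risk for less than 52 weeks, and the rate is not a Week 52 rate.

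**Step 4: Appendix C against the body text.**

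| Week 52 item | Appendix C | Body text |
|---|---|---|
| Sustained remission | ITT | Week 52 Analysis set (1.3, 1.6, 2.1.3.1, 2.3.1, 2.4.4.1) |
| Components 2 to 4 | ITT | ITT by default (2.3.1) |
| CWS and AIS | ITT, in one row with Week 24 | Week 52 Analysis set (1.6, 2.3.1, 2.4.4.2) |
| Supportive analysis excluding early-termination withdrawals | Listed for the primary endpoint | Not described in 2.4.4.1 |

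**The case against.** The strongest reply is that the 47 automatic failures need a mixed reading: the components are separate endpoints when the population is chosen, but part of the composite when the withdrawal rule is applied. If they follow the composite throughout, they belong in the Week 52 set and nobody fails by date. If they are separate throughout, they use ITT with observed data, and nobody fails automatically. The withdrawal rule is worded for the primary endpoint, and section 2.1.3.1 describes the components directly after stating the cohort limit. Section 2.4.4.1 also runs the sensitivity analysis, with its own component counts, in the manner of the primary analysis. Appendix C is weak support for ITT, since the same column is wrong in two other rows.

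Much of this stands. A reader might infer that the SAP definitely fails 47 patients and that 43.4% is a fixed ceiling. The documents do not support that as a certainty, because sections 1.6 and 2.5.3 leave an as-observed reading open. The withdrawal rule remains the more natural one: it names components 2, 3 and 4, and no other derivation of them is given.

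The reply does not rescue the population. No section places the stand-alone components in the Week 52 set, and 2.3.1 sends them to ITT without help from Appendix C. ITT fails to decompose the composite under either treatment of early stopping.

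It is also fair that the components carry no test, interval or p-value, that counts accompany the percentages, and that the Week 24 composite and components share ITT, so a coherent breakdown in all 83 exists at Week 24.

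**Conclusion.** The point holds as a mismatch of populations. Components 2 to 4 through Week 52 should not be in ITT when the composite is in the Week 52 Analysis set. Conditional on the withdrawal rule, about 47 of 83 (56.6%) fail because of randomisation date and each component is capped at about 43.4% overall; the group-level caps rest further on an assumed split of the 36. Under the as-observed reading the percentages differ materially, up to 2.3 times as large in the extreme case.

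A reader might also infer from Appendix C that the population for the Week 52 composite or for Week 52 CWS and AIS is undecided. It is not: the body text is explicit and repeated, and those entries are table errors. Nor is any p-value for the components affected, since none is planned. The harm is to interpretation and coherence, which justifies a correction but threatens no confirmatory claim.

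**What to change.** - In 2.3.1 and 2.4.4.2, state that components 2 to 4 through Week 52 are summarised in the Week 52 Analysis set under the 2.1.3.1 withdrawal rule. Keep component 1 and the Week 24 components in ITT.
- In Appendix C, replace ITT with Week 52 Analysis set for Week 52 sustained remission, Week 52 components 2 to 4, and Week 52 CWS and AIS. Leave ITT for the Week 24 entries.
- Either describe in 2.4.4.1 the supportive analysis that excludes patients withdrawn because of early termination, or delete it from Appendix C. Describing it would also cover any of the 36 whom the sponsor's decision stopped early and whom the withdrawal rule would still fail. If the 12 weeks end on 13 October 2020, the announcement was on 21 July 2020 (84 days before), and patients randomised from 24 July to 15 October 2019 had not reached Day 365 by then. Their number is not given.

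The cost is wording only, since the set is already defined. The downside is that the component percentages rest on 36 patients, as the composite already does. With the assumed split, one patient in Group B or C moves a percentage by 1/6, about 17 points.
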